11.2 Other Significant Events

Significant life events that may occur during the course of the study, including death of a loved one, loss of employment, or other hardship, may have an impact on treatment outcome. The sponsor will capture these life events using the LEC-5 measure. Such events will be entered as Comments in the eCRF and if appropriate, described in the Case Study Report for data outliers, if any.

11.3 Pregnancy

11.3.1 Definition of Childbearing Potential

A participant is considered of childbearing potential if they were assigned female at birth and are post-menarche. A participant is considered not of childbearing potential if they are premenarchal, surgically sterile (documented hysterectomy, bilateral salpingectomy, bilateral oophorectomy, and/or tubal ligation), postmenopausal, or assigned male at birth.

MP16 Protocol

Amendment 1 Version 1: 03 January 2018

11.3.2 Contraception Guidelines

Adequate birth control methods are required for participants of childbearing potential and include:

- Intrauterine device (IUD)
- Intrauterine hormone-releasing system (IUS)
- Non-oral hormonal methods, including injected, intravaginal, implanted, transdermal
- Oral hormones plus a barrier contraception (condom, diaphragm, or spermicide)
- Double barrier method (at least two of the following: condom, diaphragm, and spermicide)
- Vasectomized sole partner
- Abstinence from penile-vaginal intercourse
 - The reliability of abstinence should be evaluated carefully with the participant in relation to their general lifestyle. An additional acceptable birth control method should be discussed with the participant in case they decide to engage in penilevaginal intercourse during the course of the study.

For questions about acceptable birth control methods, contact the Medical Monitor.

11.3.3 Follow-up Requirements

Details of all pregnancies in study participants will be collected after Enrollment (Visit 0) and collected through 10 days after the last Experimental Session. Pregnancies should be reported to the sponsor via telephone or email within 24 hours of site staff awareness.

In the event of a pregnancy, the participant will discontinue Experimental Sessions but may continue with non-drug Integrative Sessions, the next CAPS-5 assessment, and Study Termination procedures. At a minimum, prior to withdrawal from the study, efforts should be made to assess the final CAPS-5 immediately and complete Study Termination procedures.

The investigator will collect follow-up information on the participant and neonate and forward to the sponsor until the outcome of the pregnancy, which will be reported on an optional Pregnancy eCRF. Any termination, elective or spontaneous, will be reported. Abnormal pregnancy outcomes, such as spontaneous abortion, fetal death, stillbirth, congenital abnormalities, or ectopic pregnancy, will be reported as SAEs.

12.0 Concomitant Medications

12.1 Tapering Instructions

The site physician will record concomitant medications during Screening. If the prospective participant is being treated with psychiatric medications at enrollment, the prospective participant will be encouraged to discuss medication tapering with their outside treating physician, if any, and will be required to give the site physician permission to do so as well. The medications will then be tapered in an appropriate fashion to avoid withdrawal effects, and discontinued at least five half-lives plus one additional week for stabilization before the first Experimental Session to avoid the possibility of any interaction. Additionally, participants who are taking prohibited opiates will be cross-tapered to an allowable opiate (hydrocodone, morphine, and codeine) under the care of their prescribing physician.

MP16 Protocol

Amendment 1 Version 1: 03 January 2018

The site physician will consult the prescribing physician to initiate medication tapering for participants, as they must refrain from taking psychiatric medications throughout the study, with some exceptions (see Section 12.2 Allowable Concomitant Medications). The prescribing physician's opinion about medication discontinuation will documented either in writing from the prescribing physician, or in writing by the site physician documenting phone contact with the prescribing physician. Tapering will follow a time course appropriate for the medication based on its half-life, with the first Experimental Session scheduled to occur after complete washout (five half-lives plus at least 1 week for stabilization).

The therapy team will request information about any changes in medication at each contact. The site physician will be responsible for reviewing and confirming all medications collected during the study.

All medications, non-prescription and prescription, will be collected from Screening through 7 days after the last Experimental Session. From 7 days after the last Experimental Session through Study Termination, only prescription or non-prescription medications taken to treat AEs will be collected. Throughout the protocol, all medications used to treat AEs will be collected, and all changes including discontinuations or additions to medications will be collected. The study team will also inquire about concomitant medication adherence and document all information on the Concomitant Medications eCRF.

Participants may return to taking psychiatric medications and discontinue birth control after the final Study Termination visit if necessary.

12.2 Allowed Concomitant Medications

The site physician may prescribe necessary and appropriate medications in accordance with local and state regulations during the study to treat AEs that do not respond to other management outlined in the Treatment Manual. Examples include concomitant benzodiazepines for uncontrolled anxiety (specifically, lorazepam at modest doses and occasional use only to avoid withdrawal effects of discontinuation between Experimental Sessions) or sleep aids (excluding trazodone) in compliance with Section 12.3 Prohibited Medications. Sublingual nitroglycerin will be available on site in the case of emergency.

Gabapentin or certain opiates will be allowed when prescribed for pain management. The following opiates will be allowed during the study: hydrocodone, morphine, and codeine. Prior to receiving study drug, participants who are taking opiates not included on this list will be cross-tapered to an allowable opiate under the care of their prescribing physician. Opiate medications may reduce the efficacy of MDMA and may prolong QT/QTc interval, but the opiates that are allowed during this trial have been selected because they have the lowest potential for QT/QTc interval prolongation. Individuals using opiates for pain management will be asked to decrease the dose leading up to the Experimental Session in order to avoid withdrawal effects when they are required to refrain from taking the medication from 12 hours before IP administration at the Experimental Session to 24 hours after. If a participant reports lack of analgesic effect during the sub-acute period following each Experimental Session, the site physician may cross-taper to a different allowed opiate medication.

If the participant is on stimulants for attention deficit/hyperactivity disorder (ADHD) at Baseline, they can continue to use them at the same dose and frequency, as long as they discontinue five half-lives before each Experimental Session and do not restart for 10 days after each Experimental Session.

All psychoactive medications, herbal supplements, nonprescription medications, and prescription medications must be reviewed by the research team. Failure to comply with protocol requirements for concomitant medications may result in withdrawal from treatment, depending on the investigator and Medical Monitor judgment.

12.3 Prohibited Medications

To be enrolled in the study, participants must:

- Refrain from the use of any psychoactive medication not approved by the research team from Baseline through Study Termination (with the exception of gabapentin or certain opiates for pain control).
- Be willing to comply with all medication requirements per protocol. Medications will only be discontinued after enrollment per clinical judgment of the site physician in consultation with the prescribing physician.
- Agree that, for 1 week preceding each Experimental Session to refrain from:
 - o Taking any specified herbal supplement (except with prior approval of the research team).
 - Taking any nonprescription medications (with the exception of non-steroidal anti-inflammatory medications or acetaminophen) unless with prior approval of the research team.
 - Taking any prescription medications (with the exception of birth control pills, thyroid hormones, or other medications approved by the research team).

MP16 Protocol Amendment 1 Version 1: 03 January 2018

Use of Marijuana, St. John's Wort, and other herbs and medicines with notable serotonergic effects are prohibited from Baseline to Study Termination. Any investigational treatments under study for PTSD treatment are prohibited from use concurrent with this study.

Diphenhydramine is excluded from this study unless prior approval is granted by the site physician.

If an SSRI, SNRI, MAOI, or other antidepressant is used between Experimental Session 1 (Visit 5) and Study Termination (Visit 20), the participant will be withdrawn from treatment and continue in follow-up.

Opiates other than hydrocodone, morphine, and codeine are prohibited from Enrollment Confirmation to Study Termination. Participants taking prohibited opiates will be cross-tapered to an allowable opiate during the Preparatory Period.

13.0 Clinical Laboratory Assessments

The site physician will confirm laboratory assessments gathered in screening for assessing eligibility. The site physician will use a list of normal ranges to conclude whether participants are eligible for the protocol and will indicate justification for admitting participants with abnormal values after consultation with the Medical Monitor.

The following laboratory assessments will be performed as a part of Screening:

- Serum electrolytes and metabolic profile
 - o Alanine aminotransferase (ALT)/serum glutamic pyruvic transaminase (SGPT)
 - Albumin:globulin (A:G) ratio
 - o Albumin, serum
 - Alkaline phosphatase, serum
 - Aspartate aminotransferase (AST)/serum glutamic oxaloacetic transaminase (SGOT)
 - o Bilirubin, total
 - o Blood urea nitrogen (BUN):creatinine ratio
 - o Calcium, serum
 - Carbon dioxide
 - o Chloride, serum
 - o Creatinine, serum
 - Globulin, total
 - o Glucose, serum
 - o Potassium, serum
 - o Protein, total, serum
 - o Sodium, serum
- CBC
 - Hematocrit
 - Hemoglobin
 - Mean corpuscular volume (MCV)
 - Mean corpuscular hemoglobin (MCH)
 - Mean corpuscular hemoglobin concentration (MCHC)
 - o Red cell distribution width (RDW)
 - Percentage and absolute differential counts
 - o Red blood cell (RBC) count
 - White blood cell (WBC) count

MP16 Protocol Amendment 1 Version 1: 03 January 2018

- Urinalysis
 - Color
 - o Appearance
 - Specific gravity
 - o pH
 - o Protein
 - Glucose
 - Ketones
 - o Occult blood
 - Leukocyte esterase
 - o Nitrite
 - o Bilirubin
 - o Urobilinogen
- Thyroid function
 - Thyroid-stimulating hormone (TSH) high sensitivity (if abnormal, free T3 and T4 will also be tested)
- HCV if indicated
- HIV serology
- %Carbohydrate deficient transferrin (%CDT) to detect heavy alcohol use
- Urine-dip pregnancy test for females of childbearing potential will be performed at the site
- Urinary drug test will be performed at the site

Laboratory assessments, with the exception of urine pregnancy and drug tests, will be performed at the nearest clinical laboratory to the site. Clinical laboratories for each site will be specified in a separate document. Certificates and normal ranges will be stored in the site's Investigator Site File (ISF).

14.0 Statistical Considerations

Key personnel, MAPS, and the biostatistician will agree on a Statistical Analysis Plan at the beginning of the study, which will provide more detail about analyses than provided in this protocol. An overview of the statistical analyses that will be performed is provided in the following sections.

14.1 Statistical Analyses

Descriptive statistics will be computed overall, as well as by initial MDMA dose received, for all available data from outcome measures, including minimum, maximum, average, median, and standard deviation.

The following analysis sets are defined for this study:

- All Enrolled: all participants who sign informed consent and are initially enrolled
- *m*ITT: all participants who receive investigational product in at least one Experimental Session and have at least one follow-up CAPS-5 assessment
- Per Protocol (PP): all participants who receive investigational product in three Experimental Sessions and have three follow-up CAPS-5 assessments
- Not Per Protocol (NPP): all participants who are included in the mITT Set but not the PP Set
- Safety: all participants who receive any IP

14.1.1 Effect Analyses

14.1.1.1 Primary Outcome Analyses

The primary analysis will be conducted after all participants complete Study Termination (Visit 20) and the study database has been locked. All outcome analyses will be based on the *m*ITT analysis set. The *de jure* estimand of treatment efficacy is of the most relevance to estimate the causal effect of three experimental sessions of MDMA-assisted psychotherapy in a controlled clinic setting on PTSD symptom severity in the intended population of patients with PTSD from any cause. The primary outcome measure, change from baseline in CAPS-5 score, will be analyzed with Mixed Model Repeated Measures (MMRM). The model will include terms for visit, baseline CAPS-5 score, and dissociative subtype (if possible). Ninety-five percent confidence intervals will be calculated for the estimated mean change from baseline CAPS-5 scores at each visit.

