8.2.2 Baseline: CAPS-5 by Independent Rater

At Visit 3, an IR will measure the Baseline CAPS-5 (referred to as Baseline CAPS-5 T1) via telemedicine as soon as possible after medication tapering, stabilization, and two Preparatory Sessions are complete. This visit may be recorded to video to establish inter-rater reliability. The scores will be sent as soon as possible to the site staff. A CAPS-5 Total Severity Score of at least 35 is required to meet Enrollment Confirmation criteria. The IR will also administer the DSP-I and SDS

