# 2.0 Introduction

This document contains a Statistical Analysis Plan (SAP) for MP16, "An Open-Label, Multi-Site Phase 2 Study of the Safety and Effect of Manualized MDMA-Assisted Psychotherapy for the Treatment of Severe Posttraumatic Stress Disorder."

MP16 tests a flexible dosing regimen of 80mg MDMA in Session 1, and 80mg or 120mg MDMA in Sessions 2 and 3, each followed by a supplemental half-dose.

The Multidisciplinary Association for Psychedelic Studies (MAPS) is a non-profit research and educational organization working to obtain approval for the prescription use of 3,4methylenedioxymethamphetamine (MDMA) in conjunction with psychotherapy in persons with posttraumatic stress disorder (PTSD). MAPS has delegated trial organization activities to its wholly owned subsidiary, MAPS Public Benefit Corporation (MPBC).

This open-label Phase 2 study will serve as a lead-in to the sponsor's two planned Phase 3 studies, only sites planned for Phase 3 will participate in these studies. This open-label lead-in Phase 2 study will serve to validate assumptions made for statistical power calculations supporting planned Phase 3 clinical trials and will provide data on the updated version of the instrument for the Primary Outcome measure, the Clinician Administered PTSD Scale for DSM-5 (CAPS-5), which will be used in Phase 3. In addition, this study will gather supportive data on the safety and effectiveness of manualized MDMA-assisted psychotherapy while providing an opportunity for clinical supervision to planned Phase 3 therapy teams. This study will be the sponsor's first multi-site studies of MDMA-assisted psychotherapy for PTSD and will explore reproducibility of findings in a multi-site format to confirm the Phase 3 study design.

This version 2 of the Statistical Analysis Plan was modified from version 1. The changes made include the following, 1) separate plans were made for each individual study, MP16 and MP17; 2) analyses were modified to be within-subject and not comparison between studies; and 3) doses used in each study were updated.

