## 6.0 Randomization and Blinding

MP16 is an open-label study with no randomization or blinding of treatment.

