## 7.0 Sample Size and Power Considerations

MP16 is a one-arm interventional study. Thus, no power nor sample size calculations were required.

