#### 8.7.1 Primary Effectiveness Analyses

The *de jure* estimand of treatment effectiveness will be used to estimate the change in CAPS-5 score from baseline due to MDMA-assisted psychotherapy on PTSD symptom severity in the intended population of patients with PTSD from any cause. The primary estimator of effectiveness will be the mean change in CAPS-5 Total Severity Scores from Baseline to 18 weeks after start of dosing (Visit 19). Least squares means from a restricted maximum likelihood (REML)-based mixed model for repeated measures (MMRM) will be used to estimate the change in CAPS-5 from baseline to each visit. CAPS-5 data collected after treatment discontinuation will not be included in the *de jure* estimand. Missing data will not be imputed.

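### The plan attributes the single-arm change in CAPS-5 and SDS to treatment, but a within-participant change without a control cannot carry that attribution

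*Protocol*

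**What the plan says.** Protocol 14.1.1.1 justifies its choice of estimand by stating that the de jure version "is of the most relevance to estimate the causal effect of three experimental sessions of MDMA-assisted psychotherapy in a controlled clinic setting". SAP 8.7.1 drops the word causal but keeps the attribution: the estimand "will be used to estimate the change in CAPS-5 score from baseline due to MDMA-assisted psychotherapy on PTSD symptom severity". SAP 8.7.2 uses the same 'due to' construction for the SDS.

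On design, SAP 7.0 states "MP16 is a one-arm interventional study" and SAP 6.0 states "MP16 is an open-label study with no randomization or blinding of treatment". SAP 2.0 records that in version 2 "analyses were modified to be within-subject and not comparison between studies". The model in Protocol 14.1.1.1 has terms for visit, baseline CAPS-5 and, if possible, dissociative subtype. It has no treatment contrast.

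On entry, Protocol 8.2.2 says "A CAPS-5 Total Severity Score of at least 35 is required to meet Enrollment Confirmation criteria". That score is taken at Visit 3. Protocol 3.1 makes the same Visit 3 score the baseline for the primary endpoint.

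**The concern.** A causal effect compares what happened with what would have happened without the treatment. Here the only comparison is with the same person's score about 18 weeks earlier. Reading the difference as an effect requires the mean score at Visit 19 to have equalled the Visit 3 mean had treatment been withheld. Neither document states or defends that assumption, and the design gives specific reasons to doubt it.

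What is at stake is what the trial may conclude. MP16 is meant partly to check the power assumptions for Phase 3 (Protocol 2.1, SAP 2.0). SAP 9.0 lets preliminary analyses inform those assumptions while the study runs, and a one-group pre-post Cohen's d is planned (Protocol 14.1.1.3, SAP 8.7.3). If the whole within-group change were read as a treatment difference, assumptions about a controlled comparison would be too optimistic.

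**Working it through.** **1. Claim against design.** Three influences on the change are built into the documents.

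- *Time.* There is no concurrent or external control, no repeat baseline and no untreated run-in against which change over about 18 weeks could be judged. Visit 3 also follows medication taper and stabilisation (Protocol 8.2.2). This is a further time-related influence, whose direction the documents do not settle.
- *Expectancy.* Participants know they receive MDMA (Protocol 9.4).
- *Regression to the mean.* Participants are kept only if the Visit 3 score is at least 35, and change is measured from that same score.

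The central raters are blinded to visit and to number of treatments (Protocol 7.1, 9.4). That limits rater bias. It does not act on the three influences above.

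**2. Size of regression to the mean.** The plan has no figure to reproduce: "MP16 is a one-arm interventional study. Thus, no power nor sample size calculations were required". The documents give no CAPS-5 mean, SD or between-visit correlation, so every input except the cut-off of 35 is an assumption. Assume baseline and follow-up are bivariate normal with equal mean μ and SD before the cut-off, correlation ρ, no treatment effect and no time effect. The expected fall among those kept is

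RTM = (1 − ρ) × SD × φ(c) / (1 − Φ(c)), with c = (35 − μ) / SD.

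Two sets of assumptions were used. Set A takes ρ as a test reliability (μ 38–46, SD 7–11, ρ 0.75–0.90). Set B takes ρ as an 18-week correlation (μ 35–45, SD 8–12, ρ 0.5–0.8), which suits a change from Visit 3 to Visit 19 better.

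| Case | μ | SD | ρ | c | φ(c)/(1−Φ(c)) | Fall in points |
|---|---|---|---|---|---|---|
| A, mildest | 46 | 7 | 0.90 | −1.571 | 0.123 | 0.10 × 7 × 0.123 = 0.09 |
| A, strongest | 38 | 11 | 0.75 | −0.273 | 0.633 | 0.25 × 11 × 0.633 = 1.74 |
| B, mildest | 45 | 8 | 0.80 | −1.250 | 0.204 | 0.20 × 8 × 0.204 = 0.33 |
| B, central | 40 | 10 | 0.65 | −0.500 | 0.509 | 0.35 × 10 × 0.509 = 1.78 |
| B, strongest | 35 | 12 | 0.50 | 0 | 0.798 | 0.50 × 12 × 0.798 = 4.79 |

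The combined range is about 0.1 to 4.8 points. Simulation under set B agreed with the formula. The earlier PCL-5 cut-off of 50 at Screening (Protocol 4.1) is not modelled. It may reduce how many are cut off at 35, but it does not remove selection on Visit 3.

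**3. Does the baseline covariate remove it?** No. In one group, with complete data and the covariate centred at its mean, the least squares mean of the change equals the raw mean change. The simulation showed the same (central case: −1.79 adjusted, against an expected −1.78).

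**4. What this does to the reported quantities.** Under set B with no effect of any kind, between 3% and 32% of participants (central case 15%) would fall by 10 points or more from baseline, the change that SAP 8.7.4 calls clinically meaningful. These percentages include ordinary fluctuation as well as regression to the mean. With 60 participants, the maximum, the 95% confidence interval for the baseline-adjusted change would lie wholly below zero in about 8% (mildest), 44% (central) and 93% (strongest) of trials, against a nominal 2.5%. An interval that excludes zero would therefore not by itself show a treatment effect.

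**The case against.** The best reply is that the quantity computed is already the right one. Protocol 3.1 and SAP 8.7.1 both specify mean change in CAPS-5 from Visit 3 to Visit 19, and the confidence interval in Protocol 14.1.1.1 is for that mean change. The causal sentence only explains why de jure was preferred to de facto, and the SAP, which gives the detail, omits the word causal and states plainly that there is one arm. This stands as far as the estimate goes: no analysis needs to change. It does not rescue the wording. 'Due to' remains in SAP 8.7.1 and 8.7.2. The de jure label settles only which data after discontinuation are used (SAP 8.2, 8.7.1) and supplies no comparator. The protocol does attach a caveat to uncontrolled change elsewhere, in the discussion of earlier Phase 2 results in 5.5, but gives none for its own primary estimand.

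A reader might infer four stronger things that the documents do not support.

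- *That the mixed-model analysis or its interval is invalid.* It is a sound description of within-participant change.
- *That regression to the mean could account for a large fall.* Every mean value computed above is below 10 points, and all rest on assumed inputs.
- *That Phase 3 will be wrongly powered, or that the study report will claim causation.* No text plans to use the whole change as a treatment difference or says how the report will word the result. The power assumptions being checked come from CAPS-4 data (Protocol 2.1), and Protocol 2.2.4 cites a between-groups effect size of 0.9.
- *That the plan credits MDMA alone.* Both documents attribute the change to the combined package of drug and psychotherapy, so the caveat must address the package.

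**Conclusion.** The attribution is wrong as written in Protocol 14.1.1.1 and in SAP 8.7.1 and 8.7.2. This conclusion needs no numerical assumption: it follows from one arm, open-label treatment, a within-participant contrast, and selection on the score that serves as baseline. The numbers only illustrate one of the three components, and that component moves with the assumed mean, SD and above all the correlation. The Phase 3 consequence is conditional on misuse of the estimate. Model, sample size and conduct are unaffected.

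**What to change.** In Protocol 14.1.1.1 and SAP 8.7.1, replace 'causal effect' and 'due to' with *mean within-participant change from V3 to V19 in participants treated with MDMA-assisted psychotherapy*. Use the same wording for the SDS in SAP 8.7.2.

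Add one sentence in each document: without a control, this change cannot be separated from time, expectancy and regression to the mean, so it is not attributable to the treatment package and should not be used as a controlled treatment difference for Phase 3 assumptions.

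Reporting a regression-to-the-mean range should not be required. It depends on the untreated 18-week correlation, which a fully treated single arm cannot estimate, so a published range would suggest precision that does not exist.

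The cost is a few sentences. The downside for the sponsor is a less favourable claim.

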- 10. Assess incidence of serious suicidal ideation and positive suicidal behavior assessed with the Columbia Suicide Severity Rating Scale (C-SSRS).
- 11. Assess mean changes in blood pressure, heart rate, and body temperature from pre-IP administration to end of each Experimental Session.

Recruitment and Participant Population

Therapy teams that have been identified to work on the sponsor's planned Phase 3 studies will treat at least one open-label participant in this study. Up to N=60 participants with a confirmed diagnosis of at least severe PTSD will be enrolled. Participants will be recruited through print and internet advertisements, referrals from other psychiatrists, psychotherapists, or physicians, and by

[figure not shown]
word of mouth. The sponsor will monitor demographics on an ongoing basis and encourage diversity in enrollment by communicating with sites.

Participants will be persons aged 18 or older, with a confirmed diagnosis of at least severe PTSD per the PCL-5 at Screening with symptoms present for at least 6 months. At Baseline, participants must qualify for a PTSD diagnosis per the CAPS-5 and have a Total Severity Score equal to or greater than 35 (severe). Participants would not be excluded for having more than one traumatic event or for having tried, not tolerated, or refused a selective serotonin reuptake inhibitor (SSRI) or serotonin norepinephrine reuptake inhibitor (SNRI) prescribed for PTSD. Participants with confirmed diagnosis of specific psychological and personality disorders will be excluded. Participants must be in good physical health and without major medical disorders that could affect the safety or tolerability of MDMA.

Statistical Analysis

All outcome analyses will be based on the *m*ITT analysis set. Change from Visit 3 (Baseline) in CAPS-5 Total Severity Scores to Visit 19 (Primary Outcome) will be analyzed with least squares means from a Mixed-Effect Repeated Measures model (MMRM). The *m*ITT analysis set will include all participants who receive IP in at least one Experimental Session and have at least one follow-up CAPS-5 assessment.

Study Structure Overview

MP16 Protocol IND #063384

Original Protocol Version 1: 18 May 2017 Amendment 1 Version 1: 03 January 2018

An Open-Label, Multi-Site Phase 2 Study of the Safety and Effect of Manualized MDMA-Assisted Psychotherapy for the Treatment of Severe Posttraumatic Stress Disorder

SPONSOR Multidisciplinary Association for Psychedelic Studies (MAPS)

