14.1.1.2 Secondary Outcome Analyses

Sheehan Disability Scale (SDS), the secondary outcome, will be analyzed in the same manner as the Primary Outcome.

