#### 8.0 Analyses

Every effort will be made to ensure complete, accurate and timely data collection and to avoid missing data, to ensure the completeness of the data which can impact the integrity and accuracy of the final study analysis. The statistical analyses will be reported using summary tables, figures, and data listings. All analyses and tabulations will be performed using SAS® Version 9.4 or higher, and S-PLUS. In general, nominal variables will be described in terms of frequencies and percentages. Ordinal and non-normal continuous variables will be described using sample median and range.

Approximately normal variables will be described using sample mean and standard deviations and analyzed by parametric statistical tests. Except for the primary effectiveness analysis, all statistical tests will be two-sided and a difference resulting in a p-value of less than or equal to 0.05 will be considered statistically significant. All p-values will be rounded to and displayed in four decimals. If a p-value less than 0.0001 occurs it will be shown in tables as <0.0001. Data not subject to analysis according to this plan will not appear in any tables or graphs, but will be included in the data listings. Selected results may be presented graphically using standard graphical software.

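### With one arm, default equal-weight LS means would report the primary CAPS-5 change for a 50:50 dissociative-subtype mix, not for the mITT set

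*Protocol*

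**What the plan says.** Protocol 14.1.1.1 bases all outcome analyses on the mITT set and describes the primary MMRM as follows: "The model will include terms for visit, baseline CAPS-5 score, and dissociative subtype (if possible". It adds: "Ninety-five percent confidence intervals will be calculated for the estimated mean change from baseline CAPS-5 scores at each visit". The protocol synopsis makes the LS mean the primary result: "Change from Visit 3 (Baseline) in CAPS-5 Total Severity Scores to Visit 19 (Primary Outcome) will be analyzed with least squares means".

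Protocol 14.0 promises a SAP "which will provide more detail about analyses than provided in this protocol". On this point the SAP gives less. Section 8.7.1 says only: "Least squares means from a restricted maximum likelihood (REML)-based mixed model for repeated measures (MMRM) will be used to estimate the change in CAPS-5". It names no model terms, no coding for subtype and no LS-mean weights. SAP 8.7.3 lists further baseline covariates that may be tried, and dissociative subtype is not among them.

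Three other statements matter:

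- SAP 7.0: "MP16 is a one-arm interventional study".
- SAP 8.0: "All analyses and tabulations will be performed using SAS" (S-PLUS is also named), with no LS-mean option given.
- Protocol 14.1.1.2, on the SDS: it "will be analyzed in the same manner as the Primary Outcome".

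**The concern.** In a two-arm additive model the weights given to the levels of a covariate cancel in the treatment difference. Here there is no difference to take. The LS mean is the result, so the weights determine which population it describes.

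A two-level class factor is the natural reading of a subtype. Protocol 14.1.1.3 lists it beside gender and ethnicity as a sub-group variable. Conventional LS means then give each level weight one half, whatever its frequency. Neither document describes the mITT set, or the wider PTSD population the estimand refers to, as half dissociative. Protocol 2.2.1 puts the subtype at 12 to 30% of people with PTSD and says such patients appear hard to treat. If they improve less, equal weighting makes the reported mean reduction too small. Because the rarer group is over-weighted, the interval is also wider.

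At stake are the primary mean change and its 95% CI, in a study whose stated purpose includes checking the assumptions behind the Phase 3 power calculations.

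**Working it through.** The plan gives no figure to reproduce, because SAP 7.0 makes no power or sample-size calculation.

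**Inputs from the documents**
- N: up to 60 (Protocol 5.1), used here as the mITT size.
- Background subtype share: 12 to 30% (Protocol 2.2.1).
- Early termination: up to 5% (SAP 8.2).
- Clinically meaningful CAPS-5 reduction: 10 points (SAP 8.7.4).

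**Assumptions (in neither document)**
- Delta, the baseline-adjusted subtype difference in change: 2.5, 5 or 10 points.
- SD of change: 12.
- Within-person correlation rho: 0.3 to 0.7.
- Share p in this trial: 12 to 40%. The upper end exceeds the background range because Protocol 7.5 links the subtype to severity and entry requires a CAPS-5 score of at least 35.

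**1. Shift in the estimate.** In the additive model (visit + baseline + subtype), the equal-weight LS mean is mu + 0.5 × Delta and the mITT-mix mean is mu + p × Delta. The shift is (0.5 − p) × Delta, the same at every visit.

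| p | 0.5 − p | Delta 2.5 | Delta 5 | Delta 10 |
|---|---|---|---|---|
| 40% | 0.10 | 0.25 | 0.5 | 1.0 |
| 30% | 0.20 | 0.5 | 1.0 | 2.0 |
| 20% | 0.30 | 0.75 | 1.5 | 3.0 |
| 12% | 0.38 | 0.95 | 1.9 | 3.8 |

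**2. Loss of precision.** With three visits, complete data and equal correlation, the variance ratio (equal weight to observed margins) is 1 + (0.5 − p)² / (p(1 − p)) × (1 + 2 rho)/3. At p = 30% and rho = 0.5 this is 1 + 0.04/0.21 × 2/3 = 1.127, an SE ratio of 1.062.

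| p | rho 0.3 | rho 0.5 | rho 0.7 |
|---|---|---|---|
| 40% | 1.011 | 1.014 | 1.017 |
| 30% | 1.050 | 1.062 | 1.073 |
| 20% | 1.140 | 1.173 | 1.204 |
| 12% | 1.315 | 1.383 | 1.447 |

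At N = 60, SD 12 and rho 0.5, the 95% CI half-width is 3.1 points with observed margins, 3.3 with equal weights at p = 30% and 3.6 at 20%.

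**3. Coverage of the mITT-mix mean (Delta 5, SD 12, rho 0.5).** The observed-margin SE is 12/√60 = 1.549.
- p = 30%: SE 1.549 × 1.062 = 1.645. Shift/SE = 1.0/1.645 = 0.61. Coverage ≈ Φ(1.35) − Φ(−2.57) = 0.91.
- p = 20%: SE 1.549 × 1.173 = 1.817. Shift/SE = 1.5/1.817 = 0.83. Coverage ≈ Φ(1.13) − Φ(−2.79) = 0.87.
- p = 40%: SE 1.549 × 1.014 = 1.571. Shift/SE = 0.5/1.571 = 0.32. Coverage ≈ Φ(1.64) − Φ(−2.28) = 0.94.

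**4. Simulation check.** REML fit, unstructured covariance, N = 60, baseline correlated with subtype, SD 12, rho 0.5, Delta 5, 5% missing at Visit 19, 1,500 runs per row (Monte Carlo SE of bias 0.04).

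| With subtype | Bias, equal weights | Bias, observed margins | SE ratio | Coverage, equal weights | Coverage, observed margins |
|---|---|---|---|---|---|
| 24/60 | +0.41 | −0.08 | 1.014 | 0.947 | 0.954 |
| 18/60 | +0.99 | −0.02 | 1.061 | 0.909 | 0.953 |
| 12/60 | +1.50 | +0.01 | 1.168 | 0.868 | 0.951 |
| 7/60 | +1.96 | −0.01 | 1.390 | 0.852 | 0.949 |

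With Delta 0 at 18/60 (1,000 runs) coverage was 0.952 with equal weights and 0.954 with observed margins, so observed margins do no harm when the subtypes do not differ.

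**The case against.** The point depends on three conditions that the documents do not settle: the term is kept, it is coded as a class factor, and the levels are weighted equally. The protocol itself makes the term optional, and the SAP may have no subtype term at all. Equal weighting is usual software behaviour, not text in the plan. This all stands, and the conclusion is conditional on it.

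The coverage figures are measured against the mITT-mix mean, whereas the estimand refers to a wider PTSD population. That also stands: observed margins are a reasonable convention for the declared analysis set and need not match the wider population. A 50:50 mix, however, is described nowhere as either one.

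The size rests on an unknown Delta, SD and correlation. At p = 40% there is almost no practical effect. At 30% a one-point shift needs Delta of 5, and one point is a tenth of the SAP's 10-point benchmark. The largest figures belong to p = 12%, about 7 of 60 participants, where the term may well be dropped, so they deserve little weight.

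Finally, there is no comparator and no success threshold, and the planned raw means (Protocol 14.1, SAP 8.7) would reveal a discrepancy. That limits the harm, but raw means do not replace the primary estimate or its CI.

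**Conclusion.** The concern holds as a conditional one. If dissociative subtype stays in the primary MMRM as a two-level class factor and LS means are computed in the conventional way, the reported CAPS-5 change and its CI describe a 50:50 subtype mix, not the mITT set. Nothing elsewhere in either document prevents this.

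The most useful range is p of 20 to 40% with an assumed Delta of 5. There the shift is 0.5 to 1.5 points, the SE is 1 to 20% larger (rho 0.3 to 0.7), and at SD 12 coverage is about 87 to 95%. The effect is zero if the term is dropped, if it enters as a 0/1 covariate held at its mean, if Delta is 0, or if p is 50%. The SDS inherits the issue. Priority is low, because no decision threshold rests on the estimate. It is still worth doing, since following the plan with default settings gives a worse primary number than an equally simple alternative.

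**What to change.** In SAP 8.7.1, list the protocol's model terms (visit, baseline CAPS-5, dissociative subtype) and state that, whenever the subtype term is kept, the visit LS means and 95% CIs are computed at the observed mITT subtype share. In SAS this is the OM option on the LS means. Entering subtype as a 0/1 covariate centred at the mITT share is equivalent. Compute the share from one record per mITT participant, so that people with more visits do not get extra weight. Say in the same place how the subtype is defined and when the term is omitted. Apply the same rule to the SDS in SAP 8.7.2.

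The weighting change costs one SAP sentence and one code option. It needs no extra data and places no burden on participants.
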